#### Visit terminology

The notation displayed in table 1 will be used for table, listing and graph (TLG) presentation of visits.

Table 1: Visits and timepoints

Notation used in the protocol	Notation used for TLG presentation
Visit 1: Screening ( $\leq$ 14 days prior to PDT)	Visit 1
Visit 2: PDT (Baseline/ treatment)	Visit 2
Visit 3: Safety Interim Visit (7 days ( $\pm$ 2 days) post-PDT)	Visit 3
Visit 4: Safety Interim Visit (14 days ( $\pm$ 2 days) post-PDT)	Visit 4
Visit 5: Final Visit (28 days ( $\pm$ 7 days) post-PDT)	Visit 5
Unscheduled visit	Unscheduled visit

#### 4.1 Dispositions of Subjects and Analysis Sets

##### Disposition of subjects and analysis sets

Descriptive analysis of subjects will be presented overall and per study site.

The disposition of subjects and analysis sets (Consented Set, Screening Failures, SAF), study visits, inclusion and exclusion criteria, and the status at study termination, together with reason for discontinuation, will be shown.

#### 4.2 Demographics and Other Covariates

##### Demographic data and baseline characteristics

Demographic data (age, sex, race and ethnicity), body measures (body height [cm], body weight [kg] ) and skin type Fitzpatrick (Type I / Type II / Type III / Type IV / Type V-VI) and Fitzpatrick skin type subgroups (Type I-III, Type IV-VI) will be tabulated.

##### Reproductive potential and pregnancy test

Details regarding reproductive potential and pregnancy tests will be listed.

##### Treatment area and assessment of AK lesions

Total area of AK target lesions ( $\geq 4$  mm) (calculated) [ $\text{cm}^2$ ] and total number of AK target lesions within the treatment field at baseline will be tabulated per subject. In addition, for AK target lesions  $\geq 4$  mm, location, diameter and automatically calculated lesion area [ $\text{mm}^2$ ] as well as severity will be tabulated per lesion.

##### Medical history and concomitant medical conditions

The proportion of subjects with relevant medical history / concomitant medical conditions will be tabulated. For medical skin history, the proportion of subjects with

- first diagnosis of AK
- AK lesions diagnosed in the past located within the selected treatment area(s)
- diagnoses of NMSC or melanoma in the past
- other relevant skin diseases

will be tabulated.

Medical History and concomitant diseases will not be coded.

##### Concomitant medication

Concomitant medications (CMs) will be coded by WHO-DD. Concomitant medications will be tabulated by anatomical therapeutic chemical (ATC) level 2, ATC level 3, and preferred name.

Concomitant medications given as pain relieving measures prior illumination will be displayed by anatomical therapeutic chemical (ATC) level 2, ATC level 3, and preferred name.

Concomitant procedures will be listed only.

#### 4.3 Study Drug Administration

PDT details (duration of incubation [min], duration of illumination [min], number and duration [min] of interruptions) will be displayed using basic statistics. Furthermore, it will be tabulated whether preparation of treatment fields, application of IMP and illumination was done according to protocol, and if illumination was performed with BF-RhodoLED® XL.

## 4.4 Analysis of Endpoints

### 4.4.1 Adverse Events

AEs will be coded by using the Medical dictionary for regulatory activities (MedDRA, MedDRA version available at the day of database closure). If an AE occurs in multiple treatment areas, it is reported separately for each treatment area within the eCRF. Thus, some AEs are counted repeatedly for the analysis.

Analysis will focus on severity and duration of TEAEs. TEAEs are defined as all AEs with onset or worsening after treatment with IMP up to Visit 5 (Final visit). AEs with start on the day of PDT which are unrelated or unlikely related to IMP belonging to AE category 'NEW LESION' and with action taken 'PDT treatment' will be classified as pre-treatment emergent adverse events. If unclear due to incomplete start date/time of AE or IMP application or uncertainty about worsening of AE, AEs will be assumed as TEAEs. AEs developing between signing the ICF and IMP application at Visit 2 will be considered as pre-treatment adverse events (PTAEs). TEAEs as defined above, will be tabulated by system organ class (SOC) and preferred term (PT) (MedDRA). The number of entries, as well as the number and rate of affected subjects will be reported for each treatment area and overall.

TEAEs will also be tabulated by relationship to IMP and/or medical device and by worst severity. TEAEs are considered being related to IMP or medical device, if causal relationship between IMP or medical device and the TEAE is at least possible or relationship assessment is missing. For AEs with changes in severity, the worst severity per AE and subject will be tabulated.

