#### 4 Statistical Evaluation

Last assessment before administration of IMP will be used as baseline value. Change from baseline will be calculated as post-baseline value(s) – baseline value. If no baseline value is available, no change from baseline will be calculated.

No replacement of missing values will be done.

Unscheduled visits will only be listed and not included in any tables except table “Subjects per visit”. Data listings of laboratory assessments will present study days. The day of treatment will be identified as Study Day 1. The day before treatment will be identified as Day -1.

All analyses will be conducted by treatment area (face / scalp / face and scalp) and overall for the safety analysis set if not stated otherwise. Selected safety analyses will be conducted overall and stratified by age groups, sex, skin type, and treatment area.

Calculation of a duration in days (e.g. duration of AE [days]) is performed as follows: stop date - start date + 1 [day]. Details of calculation of AE duration by severity are specified in section 4.4.1: Duration and severity of AEs.

Duration of illumination [min] is calculated excluding interruptions. Calculation is performed as follows: stop time - start time - duration of interruptions. (Duration of interruptions will be set to 0 if illumination was not interrupted.)

All planned analyses are of exploratory nature without any formal statistical hypotheses.

A detailed description of the planned tables, listings and graphs is given in Appendix A (version 2.0).

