#### Frequency of adverse events

An overview table showing the number of entries, as well as the number and rate of affected subjects with AEs, SAEs, TEAEs, serious TEAEs, TEAEs leading to death, TEAEs related to IMP, TEAEs related to medical device, TEAEs leading to study discontinuation, and TEAEs related to IMP or medical device will be shown.

TEAEs leading to death, serious TEAEs, TEAEs related to IMP, and TEAEs related to medical device will be presented separately.

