#### Duration and severity of adverse events

Duration of TEAEs by severity will be presented for related PTs which occurred in at least 2 subjects. For all those TEAEs (related to IMP and/or medical device), the duration of the AEs will be tabulated by severity. For each of these TEAEs, the mean duration of each severity category, based on all subjects who experienced these TEAEs, will be presented in a stacked bar chart. The proportion of days in the different severity categories as a percentage of the total duration will be presented in a frequency table for each TEAE. For the frequency table and the stacked bar charts, the calculations for each severity category will be performed with reference to all subjects who experienced this TEAE, regardless of severity. If a severity category does not occur in a subject, the duration in this category is set to 0. Calculation of duration of severity will only be done for AEs with complete start and stop dates. AEs with incomplete start or stop dates or ongoing AEs will not be considered for this analysis.

If for a TEAE only one severity is recorded during the day, then the duration of the severity of this TEAE will be set to one day. If severity changes during the day, more than one change can be recorded. For the calculation of the duration of each severity category on this day, the day will be

divided by number of changes during the day (so that duration can be e.g. 0.5 day, 0.33 day). Note that on day 1 only one severity is recorded.

Listing will include the start day of TEAEs after PDT. Calculation of TEAE start after PDT is performed in days as follows: start date of TEAE- start date of PDT.

PTAEs will be listed separately and not included in any tables or other listings.

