#### 4.4.4 Safety Assessments

##### Vital signs

The analyses of variables for vital signs will focus on

- A) the evaluation of the change from baseline (Visit 2, first measurement after the subject arrived at the site) to values on subsequent clinical visits and
- B) The evaluation of the change on Visit 2 from baseline (Visit 2, first measurement after the subject arrived at the site) to values obtained prior and after illumination (until 60 min post illumination).

Basic statistics of vital signs by visit / timepoint and of changes from baseline to post baseline visits as well as from Visit 2 baseline to values obtained prior and after illumination will be presented.

Boxplots per treatment area for Heart rate [beats/min], Systolic blood pressure [mmHg], Diastolic blood pressure [mmHg] and Body temperature [°C] on Visit 2 will be displayed stratified by measurement timepoint (at arrival / 10 min before start .... / 10 min after end ... / 60 (+/-10) min after end ...).

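### Does recording a face-and-scalp AE once per area distort the AE counts or leave the duration analysis undefined?

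*SAP*

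**What the plan says.** SAP 4.4.1 sets the recording unit: "If an AE occurs in multiple treatment areas, it is reported separately for each treatment area within the eCRF". It then states the consequence, "Thus, some AEs are counted repeatedly for the analysis", and defines what is tabulated: "The number of entries, as well as the number and rate of affected subjects will be reported for each treatment area and overall". The overview table follows the same pattern: "An overview table showing the number of entries, as well as the number and rate of affected subjects with AEs, SAEs, TEAEs". Where the severity of an AE changes, "the worst severity per AE and subject will be tabulated".

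On columns, SAP 4 says "All analyses will be conducted by treatment area (face / scalp / face and scalp) and overall for the safety analysis set". SAP 3.4 lists face, scalp, and face and scalp as a subgroup factor next to age, sex and skin type.

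On duration, SAP 4 defines the length of a single record as stop date minus start date plus one. In SAP 4.4.1, under the duration and severity heading, one clause says "the duration of the AEs will be tabulated by severity". The stacked bar chart and the frequency table are then referred to all subjects who had the TEAE, with zero days for a severity category that a subject did not have. Ongoing AEs and those with incomplete dates are left out. Protocol 14.4.3 asks for mean total duration overall and by treatment area. None of these places says how a subject's face record and scalp record of the same event are combined. SAP 4 refers table detail to Appendix A, and SAP 4.6 announces an ADaM specification; neither was available.

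**The concern.** The treatment field may lie on face, scalp or both, in several patches (Protocol 6.3), and local reactions occurred in 84-100% of subjects in earlier trials (Protocol 4.3). Two-area AEs are therefore plausible. Each would add two entries to the overall column, and no count of distinct AEs is planned, so the tables alone would not show how much repetition there is. The same would happen in the face-and-scalp column if columns group subjects by treatment field. The SAP points that way: treatment area is a subgroup factor in SAP 3.4, and it is also applied to vital signs ("Boxplots per treatment area for Heart rate"), which have no AE location.

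Duration looks more exposed, because SAP 4.4.1 names severity and duration as the focus of the AE analysis. If the tabulation is per record, a two-area AE gets double weight. If it is per subject, the two records could be summed, averaged, or merged into one run of days. These choices give different means and different shares of days by severity, and the rule is not fixed in the SAP text before results are seen.

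**Working it through.** The plan states no figure on this point, so there is nothing to reproduce. All inputs below are assumptions.

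**1. Entries against distinct AEs.** Let f be the share of subjects with a field on both areas and q the share of their local AEs that span both. Assume equal numbers of local AEs per subject. Entries per distinct local AE are 1 in single-area subjects and 1 + q in two-area subjects, so overall the ratio is 1 + f×q.

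| f | q = 0.5 | q = 1 |
|---|---|---|
| 0.1 | 1.05 | 1.10 |
| 0.3 | 1.15 | 1.30 |
| 0.5 | 1.25 | 1.50 |

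A face-and-scalp column that groups subjects would show 1.50 to 2.00; one that follows AE location would show no excess. These ratios are for local AEs only. The overall column also holds non-local AEs such as headache, so its total excess is smaller. A subject with one record and a subject with two both count once in the number and rate affected, and maximum severity per subject is the same whether one or two records are searched.

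**2. Mean duration over entries against merged AEs.** Let d1 be days in single-area subjects and d2 days in two-area subjects, with the same dates in both areas.

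- Merged: (1 − f)×d1 + f×d2
- Per entry: [(1 − f)×d1 + f×(1 + q)×d2] / (1 + f×q)

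| d1, d2 | f, q | Merged | Per entry | Difference |
|---|---|---|---|---|
| 5, 9 | 0.1, 0.5 | 5.40 | 5.57 | +3.2% |
| 5, 9 | 0.3, 0.5 | 6.20 | 6.57 | +5.9% |
| 5, 9 | 0.3, 1 | 6.20 | 6.85 | +10.4% |
| 9, 5 | 0.1, 0.5 | 8.60 | 8.43 | -2.0% |
| 9, 5 | 0.3, 0.5 | 7.80 | 7.43 | -4.7% |
| 9, 5 | 0.3, 1 | 7.80 | 7.15 | -8.3% |
| 7, 7 | any | 7.00 | 7.00 | 0% |

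**3. Combining two unequal records in one subject.** Take 100 subjects with one TEAE each, 30 of them two-area with concurrent records of 8 days (face) and 4 days (scalp); the other 70 have 8 days.

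- Sum within subject: (70×8 + 30×12)/100 = 9.2 days
- Each calendar day once: (70×8 + 30×8)/100 = 8.0 days
- Average within subject: (70×8 + 30×6)/100 = 7.4 days
- Mean over records: (70×8 + 30×12)/130 = 7.08 days

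The sum credits 12 days to a reaction that lasted 8, so it measures area-days, not how long a subject was affected. The mean over records is not on a subject basis. Counting each calendar day once, at the worst severity recorded that day, fits both the subject reference in the duration text and the worst-severity convention of SAP 4.4.1. An analyst working from the SAP has good reason to arrive there.

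**The case for a change.** The strongest argument for a change is that disclosure says repetition occurs without saying how much, and that a subject-based mean cannot be computed without some within-subject rule. The duration text already goes into detail on part-days and zero-filling, so its silence on two-area records stands out. The rule matters in the example above (7.08 to 9.2 days), and it also moves the shares of days. With an assumed face record of 3 severe days and a concurrent scalp record of 9 mild days, severe days are 3/12 = 25% if summed and 3/9 = 33% if merged at worst severity.

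Part of this stands: SAP 4.4.1 does not state the rule, and the worst-severity sentence governs frequency tables, not days. The rest is weaker. The amount of repetition can be recovered from the listings, because location is recorded for each AE (Protocol 11.3) and listings are sorted by treatment area and subject (SAP 4.7). A separate per-AE duration table is inferred from a single clause that names no unit, so double weighting is possible but not shown.

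A full merging algorithm would bring its own costs. If a merged AE counts as ongoing whenever either area record is, it leaves the duration analysis together with its completed record, which tends to remove longer events. Chained overlaps (face days 1-3, scalp 2-10, face 8-12) would need a further rule. If columns follow AE location, merged AEs would drop out of the by-area durations that Protocol 14.4.3 requires.

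**Conclusion.** No change to the plan is needed. The counting half is an open convention: a reader who wants AE frequency on a subject basis has it in the same table, and a second count of distinct AEs would be a matter of preference. The duration half is a missing derivation detail that analysts can fill sensibly and that Appendix A or the ADaM specification may already contain. Its effect cannot be sized from the documents, because neither the share of two-area subjects nor any AE duration is given; it vanishes if no AE is recorded in both areas. The study is single-arm and exploratory, so the choice cannot tilt a comparison between treatments or alter a test. This conclusion assumes that the rule used is stated with the tables and that area-level durations are kept.

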8.3 Application of BF-200 ALA

[figure not shown]
The treatment field will be localized and documented as described in [Section 6.3](#). A treatment field does not necessarily have to be continuous, but the (discontinuous) treatment field should cover a total area of approximately 60 cm² and must allow illumination in one step (see [Sections 6.3](#) and [8.4](#)).

AK lesions located outside the specified treatment field will not be considered for treatment in this study. For treatment of these AK lesions, subjects will be treated according to standard of care at the discretion of the investigator considering requirements in [Section 9](#). Most preferably, treatment of these lesions should be performed after final assessments at the end of the study (Visit 5). The treatment field should be prepared for IMP application by degreasing (using ethanol or isopropanol), removal of scabs and crusts, and if appropriate roughening of the surface, (e.g. by mild debridement). Care should be taken to avoid bleeding, especially when screened subjects report non-significant acquired or inherited coagulation defects and/or receive treatment with e.g. 81 mg acetylsalicylic acid per day or warfarin.

After this preparation, the content of three tubes of the IMP will be administered to the entire 60 cm² treatment field, covering the skin with a film of approximately 1 mm thickness. All AK target lesions should have a minimal distance of 1 cm to the border of the treatment field. The application will be performed using glove-protected fingertips or a spatula. Care should be taken to avoid that the study medication is applied to the upper and lower eyelids, the lip area (not past the vermillion border) and in the nostrils. In case of accidental contact of study medication with the eyes or mucous membranes, rinsing with water for at least 5 min will be performed.

The IMP will be allowed to dry for approximately 10 min, before a light-blocking, occlusive dressing (e.g. Tegaderm™ dressing plus aluminum foil) will be placed over the treatment field. After the incubation time of $3 \text{ h} \pm 10 \text{ min}$, the light-blocking, occlusive dressing will be removed and the remaining gel should be wiped off.

The incubation time starts when light-blocking, occlusive dressing is placed and ends with removal of the IMP. [Figure 2](#) illustrates the treatment procedure.

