10.2.4 Assessment of AK target lesions and documentation of new lesions

In this clinical trial, at least 8 AK lesions of mild to moderate intensity (according to Olsen et al., 1991) with a minimal diameter of 4 mm must be present in the treatment field. All lesions located within the treatment field including AK lesions <4 mm as well as severe AK lesions, will be treated with field-directed PDT. Lesions included in the study should be distinguishable and entirely located within the treatment field, with a minimal distance of 1 cm between the lesion margin and the border of the treatment field. However, no distance restrictions between lesions will be applied.

All AK target lesions within the treatment field have to be counted and location (treatment area) has to be documented at Visit 1. In addition, the severity of the AK target lesions ≥ 4 mm and their size should be recorded by measuring the diameters (for non-circular lesions, the largest diameter and the corresponding perpendicular diameter will be measured). AK target lesions ≥ 4 mm should also be numbered. AK target lesions <4 mm should only be counted. Total lesion area of all lesions ≥ 4 mm in the treatment field will be automatically calculated in the eCRF.

The treatment field and the location of AK target lesions should be clearly sketched in the provided cartoon. The location of the treatment field and the AK target lesions in the treatment field should also be marked on a grid foil. Furthermore, at Visit 1 any AK lesions in close proximity (< 10 cm distance) to the treatment field must be plotted on a grid foil, if applicable, for identification of new AK lesions during the course of the study. At Visit 2 new AK lesions inside or in close proximity (< 10 cm distance) to the treatment field must be documented on the grid foil, if applicable. These new AK lesions must be documented as AEs and will be treated, if located within the treatment field, but will not be considered as AK target lesions. NOTE: Occurrence of NMSC and melanoma will lead to exclusion of the subject. At further visits all new lesions (AK, NMSC, and melanoma) inside or in close proximity (< 10 cm distance) to the treatment field must be drawn in the grid foil and documented as AEs.

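### A new AK near the treatment field with an incomplete time on the day of PDT defaults to TEAE, while a matching lesion inside the field becomes pre-treatment

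*SAP*

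**What the plan says.** SAP 4.4.1 (Adverse Events) contains three rules that bear on a new lesion found at Visit 2.

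- **Special rule.** It covers "AEs with start on the day of PDT which are unrelated or unlikely related to IMP belonging to AE category 'NEW LESION", and adds a further condition: "and with action taken 'PDT treatment' will be classified as pre-treatment emergent adverse events". All the conditions must hold together.
- **General rule.** "AEs developing between signing the ICF and IMP application at Visit 2 will be considered as pre-treatment adverse events (PTAEs". It has no condition on location, relatedness or action taken.
- **Default.** "If unclear due to incomplete start date/time of AE or IMP application or uncertainty about worsening of AE, AEs will be assumed as TEAEs".

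The protocol fixes which lesions can meet the action-taken condition. Under 10.2.4, "At Visit 2 new AK lesions inside or in close proximity (< 10 cm distance) to the treatment field must be documented", so one check covers both locations. The same section then says: "These new AK lesions must be documented as AEs and will be treated, if located within the treatment field". Protocol 8.3 adds that "AK lesions located outside the specified treatment field will not be considered for treatment in this study".

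On reporting, SAP 4.4.1 (Duration and severity of adverse events) states: "PTAEs will be listed separately and not included in any tables or other listings". SAP 4.4.2 tabulates new lesions by whether they lie inside the field or within 10 cm of it. SAP 2 lists these as two separate endpoints.

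**The concern.** The special rule lets a lesion seen before treatment be classed as pre-treatment even when its clock time is not usable. It is tied to the action taken, and the action taken depends on location. Two new AKs found at the same examination, both dated that day without a time and both judged unrelated, can therefore be classified in opposite ways solely because one lies inside the field and the other beside it.

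The inside lesion then leaves the tables. The nearby one is counted as having emerged after treatment, in the TEAE tables and, reading SAP 4.4.1 and 4.4.2 together, in the table by location. A reader of that table could take the treated field to have fewer new lesions than the surrounding skin when part of the difference comes from the classification rule. In a single-arm safety study the descriptive tables are the result, so this is worth removing even though nothing is tested.

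**Working it through.** The plan gives no figure on this point, so there is none to reproduce. The check has two parts: apply the rules cell by cell, then gauge the possible size with assumed rates.

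**1. Order of events.** Neither document states outright that the Visit 2 skin check precedes IMP application, but the protocol implies it. Section 10.1.2 lists the check before field preparation. Section 10.2.4 has new AKs inside the field then treated, and has NMSC or melanoma at Visit 2 lead to exclusion. In practice, then, the point concerns new AKs.

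**2. Classification.** Take a new AK found at that check. For the inside lesion, assume it is rated unrelated or unlikely related, with action taken 'PDT treatment'.

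| What is recorded | Inside the field | Within 10 cm of the field |
|---|---|---|
| Start date before the day of PDT | PTAE (general rule) | PTAE (general rule) |
| Start on the day of PDT, times complete, before IMP application | PTAE (either rule) | PTAE (general rule) |
| Start on the day of PDT, AE time or IMP time incomplete | PTAE (special rule) | **TEAE (default)** |
| Start date too incomplete to show the day of PDT or earlier | TEAE (default) | TEAE (default) |

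Only the third row differs. If the inside lesion is rated possibly related or higher, or its relatedness is missing, it does not meet the special rule. It is then a TEAE in that row too, and the difference disappears.

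**3. Possible size.** The one input from the documents is N of about 100 (SAP 1.3). The rest are assumptions:

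- *r*: true post-PDT subject rate of new lesions, set equal in the two locations
- *v*: subject rate of new lesions at the Visit 2 check, also equal
- *u*: share of near-field Visit 2 lesions that fall in the third row
- independence of Visit 2 and post-PDT lesions, with every inside Visit 2 lesion classed as PTAE

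Tabulated inside rate = r.

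Tabulated near-field rate = 1 − (1 − r)(1 − v·u).

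Artificial excess = near-field rate − r = v·u·(1 − r).

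With r = 5%, v = 5% and N = 100:

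| u | Inside, subjects | Near field, subjects | Excess, percentage points |
|---|---|---|---|
| 0% | 5.0 | 100 × [1 − 0.95 × 1.0000] = 5.0 | 0.0 |
| 25% | 5.0 | 100 × [1 − 0.95 × 0.9875] = 6.2 | 1.2 |
| 50% | 5.0 | 100 × [1 − 0.95 × 0.9750] = 7.4 | 2.4 |
| 100% | 5.0 | 100 × [1 − 0.95 × 0.9500] = 9.8 | 4.8 |

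Over r from 2 to 10%, v from 2 to 10% and u from 0 to 100%, the excess runs from 0 to 9.8 points. The maximum is at r = 2%, v = 10%, u = 100%: 0.10 × 1 × 0.98 = 0.098. There the near-field rate is 11.8% against 2.0% inside, a ratio of 5.9.

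**4. With the condition removed.** If Visit 2 pre-IMP lesions are PTAEs in both locations, the v·u term drops out and the excess is 0 for every r, v and u.

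**The case against.** The strongest answer is that the general rule already does most of the work. It applies at any location, and the data it needs are to be collected: Protocol 11.3 asks for AE start date and time, and Protocol 8.3 records the IMP application start time. Protocol 17.1 requires an explanation for missing data, and SAP 4.6 has queries resolved before database closure. A lesion dated before the day of PDT needs no clock time, and a site that enters the time of detection satisfies the general rule. All of this stands, and it confines the problem to one row of the table.

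Two further points stand in part. Defaulting unclear timing to TEAE is a conservative convention for the overall TEAE count. That does not carry over to the split by location, where the default acts on one side only. PTAEs also remain visible in a separate listing, although a listing does not correct a table.

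A reader might infer more than the documents support, in three ways:

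- *Every near-field lesion from the Visit 2 check ends up as a TEAE.* The general rule prevents this whenever the times are usable.
- *Start times of lesions will rarely be known, and the special rule exists for that reason.* Neither document explains the rule or says how often times will be missing. An example in which all near-field lesions lack a time is the extreme of the range, not an expectation.
- *A planned comparison of inside with around is biased.* No contrast, test or estimate is specified. SAP 4.4.2 is a descriptive tabulation, and SAP 4 calls all analyses exploratory.

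**Conclusion.** The rule as written classifies by location in one situation: a new AK dated to the day of PDT, with its own start time or the IMP time incomplete, where the inside-field counterpart is rated unrelated or unlikely related. There the inside lesion is a PTAE and the near-field lesion a TEAE, although both were seen before treatment. This follows from a stated rule, not from missing detail.

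The size is unknown and may be zero. The figures above rest on assumed rates and on equal true rates in the two locations; the documents supply none of these. The direction is known: under these rules the classification can add lesions to the near-field count relative to the inside count, but cannot do the reverse. The consequence is a possible artificial near-field excess in the table by location, and lesions that pre-date treatment in the TEAE tables.

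**What to change.** Replace the special rule in SAP 4.4.1 with a sentence such as:

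> *AEs of category NEW LESION documented at the Visit 2 skin assessment before IMP application are PTAEs, whether inside or in close proximity to the treatment field and irrespective of action taken.*

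Identify these lesions from the Visit 2 skin assessment, which Protocol 10.1.2 requires in the eCRF. The AE items listed in Protocol 11.3 include location relative to the field, but none that marks detection at that assessment. If the two records cannot be linked, keep the existing criterion of start on the day of PDT and drop only the action-taken condition. That fallback is slightly broader, since it does not itself show that the lesion was seen before IMP application.

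The cost is one SAP sentence, a small linkage or data-review step before database lock, and slightly fewer near-field TEAEs. No new assessment is needed.
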